Several studies have shown that patient navigation is an effective method to increase CRC screening rates especially in minority groups with effect sizes shown in Table 2 (average of 33.7). We conservatively estimated a 44% (less than 33.7 + 20 = 54%) effect size for the PN + DVD since we will enroll patients who have previously canceled a screening colonoscopy appointment. For usual care, we used the estimate from [name], 2015 in Table 1 as it is most similar to the proposed study. See Table 5 below for summary. At 12 months, 115 in each group will yield at least 80% power for detecting the pair-wise differences (44% v. 20% v. 5%) in completion rates among the three groups using pair-wise chi-square tests or bivariate logistic regression models and a two-sided  $\alpha=.017$  level. Back-calculation, assuming an attrition rate that is approximately 25% from the sample size needed at 12 months, it requires that we approach 600 eligible subjects to enroll 450 (75% participation rate) and randomly assign them to the three intervention groups (150 per

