**Table 5. Power Analyses**

Time/Test	PN plus DVD (n=115 at 9 mos)	DVD only (n=115 at 9 mos)	Usual Care (n=115 at 9 mos)	Power
9 month/ Any Test	44%	20%	5%	.80-.99

group). By 12 months, the 150 in each intervention group will decrease to 115 through an approximate 25% attrition. The multivariable logistic regression models for the intervention effect on the CRC screening completion outcome while accounting for covariates will very likely have greater than 80% power, more than for the bivariate models because a smaller sample size is required when

covariates are added to the model. In addition, this sample size will most likely ensure greater than 80% power for other outcomes of Aim 1 (quality of bowel preparation, anxiety, and satisfaction) because they are continuous or ordinal variables. Specifically, the analysis of continuous outcomes using a general linear model will have 99% power to detect a

small effect size of .50 standard deviation units between outcome means, and the ordinal logistic regression models will have more information than the binary models.

For Aim 2, our main interest is in whether the intervention effects differ by age, race, gender, and income. We consider this aim to be exploratory as we do not have preliminary data to estimate the effect sizes; however, we feel it is important to explore interactions in this study as they may identify subgroups of patients who may not need the more intensive support of a PN. For Aim 3, the revised sample size of 115 per group will allow for the detection of mediation effects with 80% power assuming the effect sizes from the intervention to mediator and from the mediator to outcome are moderate or higher (which is what is typically assumed in a power calculation). For Aim 3, to test mediation effects, we will use the percentile bootstrap method to estimate the indirect/mediated effect. Simulations of the two-path mediation model in Mplus (Table 2) show that 115 subjects per group are needed to have 80% power to test the total indirect effect using the Sobel approach when the effect of the independent variable (the intervention variable here) on the mediator is small (.2) and independent variable on outcome is medium (.39). Using the percentile bootstrap method instead of Sobel should afford the same or greater power.

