**C.13. Data Analyses. (IR-3, IR-5, MD-3, MD-5, HT-1, HT-2, HT-3, HT-4)** Preliminary analyses will compare baseline demographic information across groups using means and standard deviations for continuous variables and frequency distributions for categorical variables. We will adjust for those characteristics in subsequent analyses if significant differences emerge at a conservative level for inclusion of a covariate ( $p < .20$ ). Characteristics of participants who drop out by 9 months will be compared with those who remain to determine what biases may exist. **(MD-4)** The above analyses will be conducted using ANOVA, chi-square tests, or exact or non-parametric equivalents. If there appear to be biases in dropout, we will conduct pattern mixture models analyses to see how the results could change based on the MAR assumption **(IR-5, MD-2, MD-3, MD-5)**. Primary analysis of outcomes will employ an intent-to-treat analysis; all participants will be included regardless of compliance with interventions. The main outcome, CRC screening completion with any test (FIT or colonoscopy) will be extracted from medical records for all participants, including those who drop out or are lost to follow-up. Intervention exposure will be measured and its effects will be accounted for in the intent-to-treat analysis. First, we will know whether participants viewed none, part, or all of the DVD. Second, we will document how many contacts PNs make to or on behalf of participants assigned to that group. These variables (viewed none/part/ or all of the DVD and number of navigator contacts) will be added as covariates in analyses. For all aims, sensitivity analysis will be conducted as needed for each outcome to assess the effects of the model assumptions on the results **(IR-5)**. Assumptions, such as normality of residuals, will be checked and appropriate modifications to the analysis plan applied if needed, such as transformations or use of non-parametric methods. From our prior studies, we expect missing data to be minimal (less than 2%) for subjects during participation. For missing data on scales, we will use mean imputation as long as two-thirds of the questions have been answered (or per validated instrument instructions, if otherwise). **(MD-2, MD-3)**

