For Aim 1, we will test the primary hypothesis related to comparing intervention effects among the three randomized groups (H1.1: PN+DVD vs. DVD only and H1.2: PN+DVD vs. usual care and DVD only vs. usual care) using the outcome of completion of CRC screening using any test at 12 months post-baseline. In addition, quality of bowel preparation, procedural anxiety, and satisfaction with the screening experience will be examined as outcomes. As an initial assessment of CRC screening completion at 12 months, we will use a chi-square test for a 3 x 2 (group by screening completion) contingency table to test whether completion rates differ across groups. If the  $p$ -value for the overall test is significant at the .05 level, pair-wise 2 x 2 tests will be conducted at the  $.05/3 = .017$  level. However, the primary analyses for Aim 1 will involve fitting multivariable logistic regression models of the primary outcome of 12-month CRC screening test completion (yes/no). Independent variables will be group assignment and continuous and categorical individual characteristics. These models will also allow us to investigate intervention effects on CRC screening test completion while adjusting for potential confounders. Group assignment will be coded using dummy variables with usual care as the reference category. For H1.3, quality of bowel preparation will be analyzed for those participants who complete colonoscopy with proportional-odds ordinal logistic regression using an ordinal dependent variable ( $1 = \text{excellent}$ ,  $2 = \text{good}$ ,  $3 = \text{fair}$ ,  $4 = \text{poor}$ ,  $5 = \text{inadequate}$ ). If some outcome categories are sparse, the outcome will be dichotomized into adequate

(*excellent or good*) versus inadequate (*fair, poor, or inadequate*). The outcomes of anxiety and satisfaction are continuous outcomes and will be modeled with linear regression.

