**Aim 2. Examine age, race/ethnicity, sex and income as potential moderators of intervention effects. (RQ-4, HT-1, HT-2, HT-3, HT-4)** We will fit multivariable models as in Aim 1, except now including interaction terms for age (< 65, age 65+), race/ethnicity (Non-hispanic Black, Non-hispanic White), sex (male, female), and annual income (<\$15,000, ≥\$15,000), respectively. Moderators will be identified by significant interaction terms in regression models. The key moderation effects of interest will be between PN+DVD vs. DVD only. Moderation of PN+DVD vs. usual care, and DVD only vs. usual care also will be examined. Hispanics will be excluded from race/ethnicity interaction tests due to small sample sizes.

**Aim 3. Examine changes in knowledge and health beliefs (knowledge, perceived risk, perceived benefits, barriers, and self-efficacy) as potential mediators of intervention effects. (RQ-6)** Mediation analysis will be conducted to identify potential mediators. Specifically, for each of the variables (changes in knowledge, perceived risk, perceived benefits, perceived barriers, and self-efficacy) mediation effects will be estimated in an logistic regression setting, fitting the appropriate mediation models using MPlus and then testing indirect effects using the percentile bootstrap approach to estimate the indirect effect. We will fit models that estimate the effects of PN plus DVD vs usual care and DVD only vs usual care, and also models that compare the strength of the indirect effects between the PN plus DVD and DVD only arms. We expect to see a difference in mediation effects mainly on barriers, with the PN plus DVD having a greater mediation effect on barriers than DVD only.

**C.14. Potential problems, strategies and benchmarks for success.** Potential problems are described below along with plans to minimize them. (*IR-6, MD-1, MD-2, MD-4*)

- *Loss to follow-up:* It is anticipated that there will be some loss to follow-up because of participant dropout, death, or relocation. Based attrition data through May 31,2019 , we estimate the loss to be approximately 25% over the 9-month study period, which has been accounted for in the revised power analysis and sample size determination.
- *Limited internal validity:* Randomization will minimize the influence of extraneous variables on outcomes.

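### C.13 puts post-randomisation exposure (DVD viewing, navigator contacts) into the intent-to-treat analysis, contradicting its own primary model and changing what the arm odds ratios estimate

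*Combined protocol and SAP*

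**What the plan says.** The first paragraph of C.13 (Data Analyses) makes the primary analysis intent-to-treat: "all participants will be included regardless of compliance with interventions". It continues: "Intervention exposure will be measured and its effects will be accounted for in the intent-to-treat analysis". It then names the two measures, how much of the DVD was viewed and how many contacts the navigator made, and says: "These variables (viewed none/part/ or all of the DVD and number of navigator contacts) will be added as covariates in analyses". Sensitivity analysis is a separate sentence after this, so the exposure covariates are not presented as sensitivity work.

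The Aim 1 paragraph of C.13 calls the chi-square tests an initial assessment and then says "the primary analyses for Aim 1 will involve fitting multivariable logistic regression models" of 12-month screening completion. Its variable list is: "Independent variables will be group assignment and continuous and categorical individual characteristics". Exposure is not on it. Aim 2 inherits whichever model is meant: "We will fit multivariable models as in Aim 1, except now including interaction terms".

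On power, C.12 gives figures for "pair-wise chi-square tests or bivariate logistic regression models" at two-sided .017, and says the multivariable models "while accounting for covariates will very likely have greater than 80% power, more than for the bivariate models".

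**The concern.** The two paragraphs of C.13 specify different models for the same primary analysis. An analyst following the Aim 1 list would estimate the effect of being assigned to an arm. An analyst following the opening paragraph would condition on what happened after assignment.

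Three features make the second model unsuitable as the primary one.

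- **Timing.** Randomisation follows the baseline interview (C.8). Viewing is asked about two weeks after the DVD is mailed, and contacts accrue after that.
- **Link to arm.** Viewing is asked only in the two DVD arms, and contacts are documented only in the navigator arm.
- **Link to outcome.** Both lie on the intended route to screening. Under C.4.b, contact count also responds to progress: there is an extra call for anyone who schedules a colonoscopy, another for anyone who requests a FIT, and otherwise as many as the participant needs. The navigator also reminds non-viewers to watch, so viewing itself can differ by arm.

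If exposure enters the model, the primary odds ratios for H1.1 and H1.2 become contrasts conditional on exposure. Their values then depend on a coding the plan does not state. There is also no rule for a missing viewing value, although C.8 anticipates missed process interviews; the imputation rule in C.13 covers scale items only.

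**Working it through.** **1. The plan's own power figures.** Inputs from C.12: rates 44%, 20% and 5%; 115 per arm; two-sided alpha .017 (z = 2.387). Power = Φ[(d − 1/n − z·SE₀)/SE₁], with SE₀ pooled, SE₁ unpooled and 1/n the continuity correction.

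- 44% vs 20%: (0.24 − 0.0087 − 2.387 × 0.0615)/0.0594 = 1.42, power 92% (Table 4: 92%).
- 20% vs 5%: (0.15 − 0.0087 − 2.387 × 0.0436)/0.0425 = 0.88, power 81% (Table 4: 80%).
- 44% vs 5%: above 99.9% (Table 4: 99%).

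Table 4 is therefore reproduced, and it rests on arm alone with no exposure term.

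**2. What the arm coefficient means.** Write the exposure-adjusted model as logit P = α + β₁·DVD + β₂·PN + γ₁·part + γ₂·all + δ·contacts. If arms without the exposure are coded none/0, β₂ − β₁ compares a navigator-arm participant with *zero* contacts to a DVD-only participant with the same viewing. C.4.b has at least two calls placed to everyone in the navigator arm, so if placed calls count as contacts, this is an extrapolation outside the data.

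**3. Hand check of the precision loss.** Assume contacts are 2 + Poisson(1) (mean 3, variance 1) and unrelated to outcome.

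- Log odds ratio for 44% vs 20%: ln 3.143 = 1.145.
- Without exposure, variance = 1/(115 × .44 × .56) + 1/(115 × .20 × .80) = 0.0353 + 0.0543 = 0.0896. SE = 0.299, and power = Φ(1.145/0.299 − 2.387) = Φ(1.44) ≈ 93%.
- With zero-coded contacts, the navigator-arm term is multiplied by 1 + mean²/variance = 1 + 9/1 = 10. Variance = 0.353 + 0.0543 = 0.407, SE = 0.638, and power = Φ(1.795 − 2.387) = Φ(−0.59) ≈ 28%.
- With 2 + Poisson(2) (mean 4, variance 2), the factor is 1 + 16/2 = 9. Variance = 0.372, SE = 0.610, and power ≈ 31%.

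**4. Simulation, PN+DVD vs DVD only.** Assumed: rates 5/20/44%; viewing none/part/all 15/15/70% in both DVD arms; contacts 2 + Poisson(1 or 2); Wald test at two-sided .017, a level the plan states for the chi-square tests and bivariate models; 1,500 replicates per configuration. Ranges cover both contact means and 115 or 150 per arm. Power is for 115, with 150 in brackets. The 150 is shown because C.13 extracts record outcomes for everyone, dropouts included.

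| Model and assumed contact pattern | Median OR | Power |
|---|---|---|
| No exposure covariates | 3.1-3.2 | 93-95% [98-99%] |
| Zero-coded, exposure unrelated to outcome | 3.2-3.3 | 28-30% [38-40%] |
| Zero-coded, one extra contact for 25% / 50% of completers | 1.5-2.0 / 0.7-1.1 | not tabulated |
| Zero-coded, one extra contact for 25% / 50% of non-completers | 5.2-6.9 / 8.8-15.0 | not tabulated |
| Centred, all of the above patterns | 3.1-3.3 | 92-95% [97-99%] |

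For DVD only vs usual care, zero-coding with exposure unrelated to outcome takes power from 86-87% to 56% [95% to 72-73%].

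*No true navigator effect (5/20/20%), zero-coded.* Extra contacts to 25% / 50% of non-completers give a false finding of benefit in 5-10% / 14-38% of trials, against about 0.4-1.1% without exposure. Extra contacts to 25% / 50% of completers give a false finding of harm in 4-8% / 10-33%. Under centring, false benefit stays under 1% in the non-completer patterns.

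*Centring when the reminder works.* Suppose viewing raises screening (assumed OR 2-4, all vs none) and the reminder raises full viewing from 70% to 85%. The centred OR is then 2.9-3.0, with power 86-87% [94-96%]. If full viewing rises from 50% to 80%, the OR is 2.4-2.7, with power 67-79% [80-91%] (1,000 replicates each).

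**5. Limiting case.** A separate simulation assumed that the whole effect runs through viewing and contacts (viewing about 16/34/50%, contacts Poisson with mean 4, zero-coded). The three arm odds ratios fell from 4.75, 15.05 and 3.17 to 0.99, 1.00 and 1.00. An intervention that worked entirely as designed would look inert.

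**6. Missing viewing.** The DVD arms enrol 2 × 150 = 300. A complete-case fit would drop 300 × 2% = 6 at C.13's expected level of missing data. It would drop 300 × 25% = 75 if the process interview were missed as often as E.1 reports attrition at six months.

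**The case against.** The strongest reply is that the Aim 1 paragraph is the specific one: it names the primary model and its variables, and exposure is not among them. The opening paragraph is general and says only that exposure goes into analyses. On that reading the primary odds ratio is the assignment effect. The difficulty is the preceding sentence, which places exposure inside the intent-to-treat analysis itself. Stretching individual characteristics to include exposure would remove the contradiction, but only by putting exposure in the primary model.

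Second, the size of the distortion is not known, even in direction. C.4.b supports extra contacts both for people moving towards screening and for people who are not, and sensible centring removes most of the problem. This is correct, and the figures above illustrate a risk; they are not a forecast. It also means that the primary result would rest on an unstated choice.

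Third, the chi-square tests contain no exposure, match the power calculation and would expose a divergence. That stands, but C.13 ranks them as an initial assessment and makes the logistic model primary, so they could reveal a conflict without settling it.

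Two narrower points stand as limits. The 25% used for missing viewing comes from a later interview and is a generous upper bound. The C.12 power remark speaks only of covariates; it is undermined only if exposure is among them and is coded unfavourably.

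**Conclusion.** The concern holds: C.13 is wrong as written. Its opening paragraph and its Aim 1 paragraph define different primary models, and the version with exposure conditions the randomised comparison on post-randomisation variables tied to arm. That model does not target the effect of assignment in H1.1 and H1.2, and Aim 2 inherits the same ambiguity.

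How far the estimate would move cannot be determined from the documents. Under the stated assumptions, the PN+DVD vs DVD odds ratio could stay near 3.2 with centred coding, or range from 0.7 to 15.0 with zero-coding. Zero-coding could also reduce power to 28-30% at 115 per arm with no bias at all. The contradiction and the change of estimand do not depend on those assumptions; only the numbers do. Because the question is which model is primary, it should be settled before analysis.

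**What to change.** In C.13:

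- State that the intent-to-treat models for Aims 1 and 2 contain assigned arm and pre-randomisation covariates only.
- Delete the sentence adding viewing and contacts as covariates, and reword the one before it so that exposure is measured and reported, not adjusted for in the intent-to-treat analysis.
- Report viewing and contacts descriptively, or in a separately labelled secondary analysis that states how exposure is coded in arms that cannot have it and how missing viewing is handled.

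The cost is a wording change to the analysis plan. Sample size, data collection and trial conduct are unchanged.

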**C.12. Sample Size, Power Analyses (RQ-2, RQ-4, IR-3).** The revised sample size estimate of 115 per group for analyses is based on ensuring adequate power for Aim 1 (see Table 4). The main objective is to compare the 12-month CRC screening rates with any test among the three groups, so the binary outcome of any CRC screening test completion at 12 months as documented in the electronic medical record has driven calculation of our sample size. For Aim 1, we will first test whether there is any overall group difference in CRC screening completion rates using a chi-square test at 5% significance level. If a significant difference is observed, pairwise comparisons will be conducted at  $\alpha=1.7\%$  (5%/3 pairwise tests) to account for multiple testing. Expected CRC screening rates, based on prior studies demonstrating the effects of computer-tailored and PN interventions, are shown in Tables 1 and 2, respectively. We have revised our DVD only effect calculations from the original estimate of 15.5% to 20% for this group. We originally proposed a DVD only effect size of 15.5% based upon the average effect size of studies listed in Table 1. This 15.5% estimate assumed that the lowest rate observed in the DVD only group might be near 20% ([name], 2015) and lowered that rate even further to 15.5% to be more conservative, as statisticians typically assume very conservative effects when doing power calculations. However, by assuming a value closer to, but still less than the lowest rate observed in the literature for a comparable population (which was 22% seen in [name], 2015 per Table 1), the samples sizes can be reduced to 115 per group for Aim 1. This sample size will afford at least 80% power for all three comparisons per Table 4 below. To allow for an approximate 25% attrition which the project is experiencing as of May 31, 2019 and still have 115 per group for analyses, a total sample size of 450 enrolled subjects is required.

**Table 4. Revising the expected rate in the DVD group to 20% (still smaller than the smallest rate for a tailored intervention in Table 1)**

Comparison	Rates	Sample Size for Groups	Power
PN+DVD vs DVD only	44% vs 20%	115 vs 115	92%
PN+DVD vs Usual Care	44% vs 5%	115 vs 115	99%
DVD only vs Usual Care	20% vs 5%	115 vs 115	80%

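### With three arms, testing each pair at .05/3 after a significant overall test at .05 is valid but needlessly strict; the overall test followed by .05 per pair already holds the family-wise error at a nominal 5%

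*Combined protocol and SAP*

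**What the plan says.** The two-step rule appears twice in the combined protocol and SAP. In C.12, "we will first test whether there is any overall group difference in CRC screening completion rates using a chi-square test at 5% significance level". The section goes on: "If a significant difference is observed, pairwise comparisons will be conducted at". The level named there is 1.7%, explained as ("5%/3 pairwise tests) to account for multiple testing"). C.13, under Aim 1, repeats it. Once the three-group chi-square has passed at .05, the text says "pair-wise 2 x 2 tests will be conducted at the", and the level it names is one third of .05, rounded to .017.

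The sample size uses that level. C.12 claims 80% or more "power for detecting the pair-wise differences (44% v. 20% v. 5%) in completion rates among the three groups". The calculation assumes testing "using pair-wise chi-square tests or bivariate logistic regression models and a two-sided", with .017 as the level. Table 4 gives 92%, 99% and 80% for PN+DVD versus DVD, PN+DVD versus usual care, and DVD versus usual care, at 115 per arm. C.12 concludes: "This sample size will afford at least 80% power for all three comparisons per Table 4 below".

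Two further statements in C.13 matter. It presents the chi-square sequence as an initial assessment and names multivariable logistic regression as the primary analysis for Aim 1, with no overall test and no pairwise level stated for those models. It also says the main outcome will be taken from medical records for everyone, including participants lost to follow-up.

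**The concern.** The overall test and the division by three are two protections against the same risk: a false claim among three pairwise contrasts on one outcome. With three arms either is enough by itself. Using both costs power, and the cost falls hardest on DVD versus usual care, which has the lowest power in Table 4. At stake is a higher chance of missing a real DVD effect, or of failing to separate PN+DVD from DVD (Hypothesis 1.1), with no error control that a nominal 5% family-wise rate requires.

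**Working it through.** **Inputs.** From C.12 and C.13: rates 44% (PN+DVD), 20% (DVD) and 5% (usual care); 115 analysed and 150 enrolled per arm; overall test at .05; pairs at .05/3, two-sided.

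**1. Reproduce Table 4.** Normal approximation with pooled null variance and continuity correction 1/n:

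power = Φ{[d − 1/n − z·s₀]/s₁}, with s₀ = √[2p̄(1−p̄)/n] and s₁ = √[(p₁q₁ + p₂q₂)/n].

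- DVD vs usual care, n = 115: d = .15, 1/n = .0087, p̄ = .125, s₀ = .0436, s₁ = .0425. At .05/3, z = 2.394: (.15 − .0087 − 2.394 × .0436)/.0425 ≈ 0.87, power 80.7%.
- PN+DVD vs DVD: d = .24, p̄ = .32, s₀ = .0615, s₁ = .0595. (.24 − .0087 − 2.394 × .0615)/.0595 ≈ 1.41, power 92.1%.
- PN+DVD vs usual care: above 99.9%.

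These match Table 4's 80%, 92% and 99%, reading 99% as a cap. Table 4 is correct at its stated level.

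**2. Same formula at .05 (z = 1.960).** DVD vs usual care: 1.31, power 90.6%. PN+DVD vs DVD: 1.86, power 96.9%. The n per arm giving 80% power for DVD vs usual care falls from 114 to 88.

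**3. Why .05 per pair is enough after the overall test.** Let the pairwise nulls be A = B, A = C and B = C.
- If any two are true, all three arms are equal. That is the global null, which the overall test covers at .05, so no pair can be falsely rejected more often than the overall test rejects.
- If the global null is false, at most one pairwise null is true, and it is tested once, at .05.

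This is closed testing for three groups. Since p < .0167 implies p < .05, it rejects everything the plan's rule rejects.

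**4. Family-wise error.** Pearson tests, n = 115, 500,000 simulated trials per scenario:

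| True rates (%) | Overall test + .017 | Overall test + .05 |
|---|---|---|
| 20/20/20 | .041 | .050 |
| 5/5/5 | .032 | .046 |
| 44/20/20 | .016 | .050 |
| 44/5/5 | .013 | .047 |
| 44/44/5 | .017 | .054 |

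The .054 is the finite-sample size of one unadjusted Pearson test at 44% vs 44%, not a failure of closure. The overall test must be binding: pairs at .05 without it give .122 at 20/20/20.

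**5. Power, simulated Pearson tests, full procedure.**

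| Comparison | n = 115: .017 → .05 | n = 150: .017 → .05 |
|---|---|---|
| DVD vs usual care (20 vs 5) | 88% → 95% | 95.7% → 98.5% |
| PN+DVD vs DVD (44 vs 20) | 94% → 98% | 98.4% → 99.5% |
| All three pairs | 83% → 93% | 94% → 98% |
| DVD vs usual care at 15.5 vs 5 | 62% → 78% | 75% → 87% |

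PN+DVD vs usual care is essentially 100% throughout. The 15.5% row uses the DVD rate that C.12 has since replaced, so it is a sensitivity case only.

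**6. Which step costs the power.** At the design rates, power at .017 is the same with and without the overall test, which itself passes almost always. At weaker rates assumed here for range (30/20/12 and 26/22/18), the overall test costs at most about 0.5 point. The loss comes from the .017 level.

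**The case against.** The strongest reply is that nothing is broken. The trial was sized at .017, Table 4 already carries that cost, every pair reaches 80% under the plan's assumptions, and type I error is not inflated. That stands. So does the point about records: if the outcome is obtained for all 150 per arm, the gain at the design rates shrinks to about 3 points for DVD versus usual care and 1 point for PN+DVD versus DVD. The larger gains need weaker true rates than the plan assumes.

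Four stronger readings are tempting, and the documents do not support them.
- *A double penalty.* Two devices are stacked, but the overall test costs almost nothing; only the .017 level has a price.
- *An underpowered trial.* Table 4 reproduces and meets its 80% target.
- *A primary analysis that loses power to .017.* C.13 attaches the rule to an initial assessment and gives no level for the primary logistic models. C.12 names .017 for chi-square or bivariate logistic tests. The plan leaves the rule for the primary contrasts unstated, so their loss cannot be read from the text.
- *No multiplicity protection needed.* Closure covers three contrasts on one outcome. Hypotheses 1.1 and 1.2 also name FIT and colonoscopy separately, and neither this argument nor the plan's .05/3 covers those.

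Timing is also a fair objection. C.12 uses data through May 31, 2019, so the trial is under way, and relaxing a threshold now needs justification and a dated record.

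**Conclusion.** The Bonferroni step is redundant once the overall test is passed, and removing it is a cheap improvement rather than a correction. At 115 per arm and 44/20/5% it adds about 7 points of power for DVD versus usual care (10 on Table 4's basis), about 4 for PN+DVD versus DVD, and about 10 for winning all three pairs. At 150 per arm these two pairs gain about 1 to 3 points each; at a 15.5% DVD rate, DVD versus usual care gains 16 points (n = 115) or 12 (n = 150).

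This rests on exactly three arms, one outcome (any-test completion at 12 months), a binding overall test, and overall and pairwise tests from the same analysis. The figures are for unadjusted chi-square tests; covariate-adjusted logistic contrasts will differ somewhat. Error control is nominal, with finite-sample departures such as the .054 above.

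**What to change.** In C.12 and C.13, replace the pairwise rule with one sentence: for any-test completion at 12 months, a 2-df overall test of group in the primary logistic model at two-sided .05 gates the three pairwise contrasts from that same model, each tested at two-sided .05. This also supplies the rule that C.13 leaves unstated for the primary analysis. Say explicitly that FIT-only and colonoscopy-only comparisons fall outside this procedure.

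Restate Table 4 at .05. On its present continuity-corrected basis the entries become about 97%, above 99% and 91%.

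The cost is a sentence in each section and a revised table, with no added participants. There are two small downsides. Tests at .05 will not match Bonferroni simultaneous intervals, so show 98.3% intervals as well if those are wanted. And the change comes mid-trial, so record it, with its reason, before anyone sees outcomes by arm.
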